**E2112 specific expedited reporting requirements:**

- **Thrombocytopenia**

Any  $\geq$  grade 4 platelet count must be reported via CTEP-AERS within 24 hours of learning of the event followed by a complete expedited report within 5 calendar days of the initial 24-hour report.

Any grade 3 platelet count with significant bleeding, regardless of whether or not the patient was hospitalized, must be reported via CTEP-AERS within 10 calendar days of learning of the event.

- **Pregnancy**

Pregnancies and suspected pregnancies (including a positive pregnancy test regardless of age or disease state) occurring with a female patient while the subject is on Entinostat/Placebo, or within 3 months of the subject’s last dose of Entinostat/Placebo, are considered immediately reportable events. **The pregnancy, suspected pregnancy, or positive pregnancy test must be reported via CTEP-AERS within 24 hours of the Investigator’s knowledge.** Please refer to [Appendix VIII](#) for detailed instructions on how to report the occurrence of a pregnancy as well as the outcome of all pregnancies.

**E2112 specific expedited reporting exceptions:**

Rev. 10/16

The adverse events listed below **do not** require expedited reporting via CTEP-AERS:

- If an AE meets the reporting requirements of the protocol, and it is listed on the SPEER, it should **ONLY** be reported via CTEP-AERS if the grade being reported exceeds the grade listed in the parentheses next to the event. The only exception is that platelet count decrease (thrombocytopenia) must be reported via CTEP-AERS as outlined above.

5.2.8 Other recipients of adverse event reports and supplemental data

DCTD/NCI will notify ECOG-ACRIN/pharmaceutical collaborator(s) of all AEs reported to the FDA. Any additional written AE information requested by ECOG-ACRIN MUST be submitted to BOTH the NCI and ECOG-ACRIN.

Adverse events determined to be reportable via CTEP-AERS must also be reported by the institution, according to the local policy and procedures, to the Institutional Review Board responsible for oversight of the patient.

5.2.9 Second Primary Cancer Reporting Requirements

All cases of second primary cancers, including acute myeloid leukemia (AML) and myelodysplastic syndrome (MDS), that occur following treatment on NCI-sponsored trials must be reported to ECOG-ACRIN using Medidata Rave.

- **A second malignancy is a cancer that is UNRELATED to any prior anti-cancer treatment (including the treatment on this protocol).** Second malignancies require ONLY routine reporting as follows:
  1. Complete a Second Primary Form in Medidata Rave within 14 days.
  2. Upload a copy of the pathology report to ECOG-ACRIN via Medidata Rave confirming the diagnosis.
  3. If the patient has been diagnosed with AML/MDS, upload a copy of the cytogenetics report (if available) to ECOG-ACRIN via Medidata Rave.
- **A secondary malignancy is a cancer CAUSED BY any prior anti-cancer treatment (including the treatment on this protocol).** Secondary malignancies require both routine and expedited reporting as follows:
  1. Complete a Second Primary Form in Medidata Rave within 14 days.
  2. Report the diagnosis via CTEP-AERS at <http://ctep.cancer.gov>
    - Report under a.) leukemia secondary to oncology chemotherapy, b.) myelodysplastic syndrome, or c.) treatment related secondary malignancy

3. Upload a copy of the pathology report to ECOG-ACRIN via Medidata Rave and submit a copy to NCI/CTEP confirming the diagnosis.
4. If the patient has been diagnosed with AML/MDS, upload a copy of the cytogenetics report (if available) to ECOG-ACRIN via Medidata Rave and submit a copy to NCI/CTEP.

**NOTE:** The Second Primary Form and the CTEP-AERS report should not be used to report recurrence or development of metastatic disease.

**NOTE:** If a patient has been enrolled in more than one NCI-sponsored study, the Second Primary Form must be submitted for the most recent trial. ECOG-ACRIN must be provided with a copy of the form and the associated pathology report and cytogenetics report (if available) even if ECOG-ACRIN was not the patient's most recent trial.

**NOTE:** Once data regarding survival and remission status are no longer required by the protocol, no follow-up data should be submitted via CTEP-AERS or by the Second Primary Form.

Rev. Add6

[Redacted text block]

[http://ctep.cancer.gov/protocolDevelopment/electronic\\_applications/docs/ae guidelines.pdf](http://ctep.cancer.gov/protocolDevelopment/electronic_applications/docs/ae guidelines.pdf)

Rev. 10/15  
Rev. Add5

[Redacted text block]

5.2.7

[Redacted]			[Redacted]
[Redacted]	[Redacted]	[Redacted]	[Redacted]
[Redacted]	[Redacted]	[Redacted]	[Redacted]
[Redacted]	[Redacted]	[Redacted]	[Redacted]
[Redacted]	[Redacted]	[Redacted]	[Redacted]
[Redacted]	[Redacted]	[Redacted]	[Redacted]
[Redacted]	[Redacted]	[Redacted]	[Redacted]
[Redacted]	[Redacted]	[Redacted]	[Redacted]
[Redacted]	[Redacted]	[Redacted]	[Redacted]
[Redacted]	[Redacted]	[Redacted]	[Redacted]
[Redacted]	[Redacted]	[Redacted]	[Redacted]
[Redacted]	[Redacted]	[Redacted]	[Redacted]
[Redacted]	[Redacted]	[Redacted]	[Redacted]
[Redacted]	[Redacted]	[Redacted]	[Redacted]
[Redacted]	[Redacted]	[Redacted]	[Redacted]
[Redacted]	[Redacted]	[Redacted]	[Redacted]

[Redacted]			[Redacted]
[Redacted]	[Redacted]	[Redacted]	[Redacted]
	[Redacted]		[Redacted]
[Redacted]			[Redacted]
[Redacted]			[Redacted]
	[Redacted]		[Redacted]
	[Redacted]		[Redacted]
[Redacted]			[Redacted]
	[Redacted]		[Redacted]
	[Redacted]		[Redacted]
[Redacted]			[Redacted]
[Redacted]			[Redacted]
	[Redacted]		[Redacted]
[Redacted]			[Redacted]
	[Redacted]		[Redacted]
[Redacted]			[Redacted]
[Redacted]			[Redacted]
	[Redacted]		[Redacted]
	[Redacted]		[Redacted]
[Redacted]		[Redacted]	[Redacted]

[Redacted]

[[contact]](mailto:[contact])

[Redacted]

[Redacted]

[Redacted]

[Redacted]

[Redacted]

[Redacted]

[Redacted]

[Redacted text block]

Rev.4/15

## 5.4 Dose Modifications

Although entinostat and exemestane have distinct toxicity profiles, they do share some adverse events such as fatigue, nausea, and diarrhea. There is the theoretical possibility that one agent may potentiate the other and hence drug causality will not always be clear. In the event of uncertainty, dose reductions and/or delays will follow the most conservative approach.

Treatment will be modified based on treatment-related toxicity as described below for all patients receiving entinostat/placebo. Dose omits due to toxicity will not be made-up; patients may resume treatment once toxicity resolves as per the regular schedule. Dose reductions due to toxicity are permanent. Dose escalation is not allowed.

If more than two doses of entinostat/placebo are omitted in a single cycle due to entinostat/placebo-related toxicity, the patient will be permanently discontinued from protocol therapy, followed until event resolution, and managed at the investigator's discretion. Exemestane may continue in this case.

Regular dosing and compliance with medication is strongly encouraged. If  $\geq 2$  doses of entinostat/placebo per cycle are omitted for reasons other than toxicity in  $> 2$  cycles, the patient will discontinue protocol therapy. However, if the treating investigator believes the subject is benefitting from treatment and feels it is in the best interest of the participant to continue on study, exceptions may be considered after discussion with the Study Chair.

Prior to administration of first dose of entinostat/placebo in each cycle, patient's organ function must have recovered to the following values:

Minimum Values for Dose Administration	
Absolute Neutrophil Count	$\geq 1 \times 10^9/L$
Platelets	$\geq 50 \times 10^9/L$
Creatinine	$\leq 2 \times$ institutional upper limit of normal (ULN)

**NOTE:** The dose modifications noted below refer to administration of entinostat/placebo. Exemestane dose reductions are not allowed. If exemestane administration is held for any reason, patient can remain on study for up to 7 days. If exemestane administration is held for  $> 7$  days, patient will be considered off protocol treatment.

**All toxicity grades below are described using the NCI Common Terminology Criteria for Adverse Events (CTCAE) version 4.0.**

**All appropriate treatment areas should have access to a copy of the CTCAE version 4.0. A copy of the CTCAE version 4.0 can be downloaded from the CTEP website (<http://ctep.cancer.gov>).**

Rev.4/15

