## 5. Treatment Plan

### 5.1 Administration Schedule

Cycle = 4 weeks (28 days)

Rev.4/15

A complete cycle of treatment is defined as 28 days ( $\pm$  3 days) of once daily continuous treatment of exemestane in combination with entinostat/placebo. A new cycle start is defined as the first planned date of entinostat/placebo for the cycle.

Rev. 10/16

Entinostat/placebo should be taken on an empty stomach, at least 1 hour before and 2 hours after a meal/snack. Missed doses should not be made up later.

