**Table 5.4.1: Dose Reductions for Entinostat/Placebo-Related Toxicity**

Hematologic Toxicity			
CTCAE System Organ Class (SOC)	Adverse Event	Grade	Entinostat/Placebo Dose Change
Investigations	Neutrophil count decreased	Grade 1 or 2	No change
		Grade 3 or 4	Omit for 2 weeks and reduce to 3mg
	Platelet count decreased	Grade 1 or 2	No change
		Grade 3 or 4	Omit for 2 weeks and reduce to 3mg
	White blood cell decreased	Grade 1 or 2	No change
		Grade 3 or 4	Omit for 2 weeks and reduce to 3mg
Non-Hematologic Toxicity			
CTCAE System Organ Class (SOC)	Adverse Event	Grade	Entinostat/Placebo Dose Change
Gastrointestinal disorders	Diarrhea (Reduce dose only after optimal use of loperamide)	Grade 1 or 2	No change
		Grade 3 or 4	Omit for 2 weeks and reduce to 3mg
	Nausea / Vomiting (Reduce dose only after optimal use of anti-emetics)	Grade 1 or 2	No change
		Grade 3 or 4	Omit for 2 weeks and reduce to 3mg
Metabolism and nutrition disorders	-Hyperglycemia -Hypoglycemia -Hypophosphatemia -Hypernatremia -Hyponatremia -Hypercalcemia -Hypocalcemia	Grade 1 or 2	No change
		Grade 3 or 4	Omit for 2 weeks and reduce to 3mg
Other non-hematologic adverse events not mentioned above		Grade 1 or 2	No change
		Grade 3 or 4	Omit treatment until toxicity resolves to Grade 1 then dose reduce to 3mg

Unless otherwise specified, grade 3 or 4 toxicity should improve to grade 2 or better prior to resuming treatment

---

If more than two doses of entinostat/placebo are omitted in a single cycle due to entinostat/placebo-related toxicity, the patient will be permanently discontinued from protocol therapy

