## 7. Study Parameters

1. Baseline evaluations within 4 weeks prior to randomization unless specified.
2. Prestudy scans and x-rays used to assess all measurable or non-measurable sites of disease must be done  $\leq$  4 weeks prior to randomization.
3. Prestudy CBC (with differential and platelet count) and all required prestudy chemistries must be done  $\leq$  4 weeks before randomization, as outlined in Section [3](#).

	Baseline	Cycle 1 Day 15	End of Cycles 1 and 2	End of Cycle 3	End of each cycle (cycle 3-forward) 	Every 3 cycles (cycle 3, 6 etc)	At discontinuation of treatment 	Post treatment 
History, Physical Exam, ECOG PS, Vital signs, Height, Weight	X 		X	X	X		X	X
Symptom/Toxicity assessments	X 		X	X	X		X	
CBC 	X	X	X	X	X		X	
Chemistries 	X	X	X	X		X	X	
Serum estradiol 	X							
ECG	X							
Bone scan 	X			X		X		X 
Tumor assessment by CT or MRI 	X			X		X	X	X 
Serum or Urine Pregnancy Test 	X							
PRO Assessments 	X			X		X	X	X
PRO Assessment: FBSI 	X		X	X	X			
PRO-CTCAE 	X		X	X	X		X	
Exemestane 				X (daily)				
Entinostat/placebo 				X (weekly)				
LHRH agonist (pre/perimenopausal female and all male participants only) 				X (monthly)				
Pill Count/Diary 			X	X	X	X	X	
Concomitant Medications	X		X	X	X		X	X 
Biological Sample Submissions [See Sections 11 and 12 ]								
Whole blood, one (1) 8mL CPT citrate tube 	X	X						

	Baseline	Cycle 1 Day 15	End of Cycles 1 and 2	End of Cycle 3	End of each cycle (cycle 3-forward) 	Every 3 cycles (cycle 3, 6 etc)	At discontinuation of treatment 	Post treatment 
FFPE tumor tissue (primary & metastatic) 	X							
Whole blood, one (1) 8mL ACD yellow top 	X							

	Cycle 1, Day 1 [2 samples drawn at least 2 hours apart, 2-5 hours after dosing]	Cycle 1, Day 15 [1 sample drawn 1 hour after dosing]	Within 72 hours prior to the start of Cycle 2
Population Pharmacokinetics [OPTIONAL PER PATIENT CONSENT]: Plasma, one (1) 6mL K2EDTA lavender top tube per time point 	X	X	X

- Physical exam, ECOG PS, vital signs, and symptom/toxicity assessment must be performed ≤ 2 weeks before randomization.  

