**NOTE:** Height measurements may have been taken > 4 weeks from baseline.
- CBCs, which includes WBC, ANC, Platelets, Hgb, and Hct required for protocol therapy must be done ≤ 72 hours prior to Cycle 2 and every cycle thereafter. Baseline CBCs do not need to be repeated prior to Cycle 1 Day 1.
- Albumin, alkaline phosphatase, total bilirubin, bicarbonate, BUN, calcium, chloride, creatinine, glucose, magnesium, phosphorus, potassium, total protein, SGOT (AST), SGPT (ALT), sodium must be done ≤ 72 hours prior to Cycles 2-4 and every 3 cycles thereafter. Baseline chemistries do not need to be repeated prior to Cycle 1 Day 1.
- Only required for women age < 55 years and with intact ovaries as described in Section [3.1](#).
- Baseline bone scan required in all patients.  
**NOTE:** If bone scan done ≤ 6 weeks prior to registration showed no evidence suggesting bone metastases and no clinical indication of skeletal pain or other evidence suggesting bone metastases, a repeat baseline bone scan is not required.
- CT of the chest and CT or MRI of abdomen/pelvis are required at baseline. Subsequent imaging for the subject should be conducted on the same scanner using the same acquisition and reconstruction parameters. Those tests required to follow known site(s) of disease must be repeated at the end of 12 weeks from randomization and then every 12 weeks (3 cycles) during treatment and according to the follow up schedule if off treatment, until first progression of disease. **NOTE:** All tumor assessment should be scheduled based on calendar time (every 12 weeks) and not cycle length. Image thickness (reconstructed) should be 5 mm or less for CT and MRI, and contiguous slices are preferred to those with intervening gaps. Consistent use of contrast agent, dose, and injection parameters (including time of image collection after contrast) are recommended. See Section [10](#) for additional details and submission instructions.  
**NOTE:** If the CT of the chest and CT or MRI of abdomen/pelvis done ≤ 6 weeks prior to randomization showed no evidence of disease in the area(s) and no clinical indication suggesting new metastases, full re-staging including all areas is not required; however, ensure that disease is evaluable per RECIST 1.1 requirements (Section [6](#)).
- Patient-Reported Outcomes to be assessed at the following time (see Section [5.6](#) for detailed instructions):

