PROMIS Fatigue, FAACT, FACIT-D: Baseline (before Cycle 1 Day 1), end of Cycle 3, end of Cycle 6, end of Cycle 12, at end of protocol treatment, including treatment discontinuation for any reason (i.e., toxicity, progression, completion of protocol therapy) and 4 weeks after end of protocol treatment, including treatment discontinuation for any reason (i.e., toxicity, progression, completion of protocol therapy).

Rev. 10/16 The ECOG-ACRIN Medication Adherence Scale Modified from the Morisky Index: end of Cycle 3, end of Cycle 6, end of Cycle 12, and at  
Rev. Add7 end of protocol treatment, including treatment discontinuation for any reason (i.e. toxicity, progression, completion of protocol therapy).  
Please note there will be one Medication Adherence Scale form completed for each agent (entinostat/placebo and exemestane).

FACT-G: Baseline (before Cycle 1 Day 1), end of Cycle 3, end of Cycle 6, end of Cycle 12, and at end of protocol treatment, including treatment discontinuation for any reason (i.e. toxicity, progression, completion of protocol therapy).

8. The FBSI will be administered at baseline, end of each cycle for the first six months after randomization, and then at the end of Cycles 8, 10, and 12. After Cycle 12, the FBSI will be administered on the same schedule as Tumor assessments until disease progression.
9. Pill counts for entinostat/placebo and diaries for exemestane should be collected at the end of each cycle until discontinuation of study treatment.
10. Repeat any test not done  $\leq$  the prior 28 days.
11. Every 3 months if patient is  $< 2$  years from study entry, every 6 months if patient is 2-5 years from study entry, and annually if patient is  $>5$  years from study entry. No specific requirements if patient is more than 10 years from study entry.
12. Tumor assessments are to be done up to (and including) the assessment which shows first progression of disease. If patient discontinues treatment due to reasons other than disease progression, concomitant medication and tumor assessments should be performed until disease progression on the following schedule: Every 3 months if patient is  $< 2$  years from study entry, every 6 months if patient is 2-5 years from study entry, and annually if patient is  $>5$  years from study entry. No specific requirements if patient is more than 10 years from study entry.

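### Section 5.4 sets a creatinine limit for the first entinostat/placebo dose of every cycle, but from Cycle 5 the calendar clearly schedules creatinine at only one cycle start in three

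*Combined protocol and SAP*

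**What the plan says.** Section 5.4 (Dose Modifications) states when organ function must have reached the minimum values in its table: "Prior to administration of first dose of entinostat/placebo in each cycle". The table lists neutrophils, platelets and creatinine (at most 2 x institutional ULN).

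Section 7 (Study Parameters) sets the tests:

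- **CBC, footnote 2:** "required for protocol therapy must be done ≤ 72 hours prior to Cycle 2 and every cycle thereafter". This supplies neutrophils and platelets.
- **Chemistries, footnote 3:** the panel that contains creatinine "must be done ≤ 72 hours prior to Cycles 2-4 and every 3 cycles thereafter".
- **Calendar:** the Chemistries row is blank in the column headed "End of each cycle (cycle 3-forward" and marked in the every-3-cycles column. The CBC row is the reverse.
- **Footnote 10**, attached to the per-cycle and discontinuation columns: "Repeat any test not done" within the previous 28 days. It names no particular test.

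Table 5.4.1 names no renal event. A raised creatinine would fall under "Other non-hematologic adverse events not mentioned above", a row that changes the dose only at Grade 3 or 4.

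**The concern.** A condition worded as mandatory at every cycle start should have a test that supplies the value at every cycle start. Two of the three Section 5.4 minimums have one; creatinine does not. A site that follows the calendar exactly can reach Cycle 5, 6, 8, 9, 11 or 12 with no current creatinine against which to check the rule. Sites that read footnote 10 differently will test at different frequencies.

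The pre-cycle minimum is also the only dose rule that names creatinine, so there is little behind it if it goes unchecked. Many patients reach the affected cycles. Under the Section 9.2.1 exponential PFS assumptions (medians 4.1 and 7.1 months), the proportion progression-free at the Cycle 5 start (4 x 28 = 112 days, about 3.68 months) is 0.5^(3.68/4.1) = 54% on placebo and 0.5^(3.68/7.1) = 70% on entinostat. Fewer will still be on treatment, because some stop for other reasons.

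**Working it through.** The plan gives no figure of its own to reproduce. The check sets the starts where Section 5.4 needs a creatinine beside those where Section 7 supplies one.

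**Inputs.** Panel schedule: footnote 3. Draw lead: 0 to 3 days before the cycle (the 72-hour window). Cycle length: Section 5.1, "A complete cycle of treatment is defined as 28 days", with a window of 3 days either way, so 25 to 31 days.

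**Coverage, Cycles 2 to 13**

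| | Cycle starts | Count |
|---|---|---|
| Creatinine needed (5.4) | 2 to 13 | 12 |
| Panel scheduled (footnote 3) | 2, 3, 4, 7, 10, 13 | 6 |
| No panel scheduled | 5, 6, 8, 9, 11, 12 | 6 |

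From Cycle 5 to Cycle 13, 3 of 9 starts are covered; to Cycle 25, 7 of 21. Both are one in three. The calendar agrees with the footnote, so this does not come from a misread table.

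**Age of the last value if footnote 10 covers only the rows marked in its column**

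- At the Cycle 5 start: 25 + 0 to 31 + 3 = 25 to 34 days.
- At the Cycle 6 start: 2 x 25 + 0 to 2 x 31 + 3 = 50 to 65 days.
- Between the pre-Cycle 4 and pre-Cycle 7 panels: 3 x 25 - 3 to 3 x 31 + 3 = 72 to 96 days.
- Neutrophils and platelets at the same starts: at most 72 hours.

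**If footnote 10 covers every test**

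Age at the end-of-cycle visit = cycle length + draw lead - visit lead.

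- With a 28-day cycle and equal leads (0/0, 1/1, 2/2 or 3/3 days) this is exactly 28, so no repeat is due. The value is then 28 + 0 to 28 + 3 = 28 to 31 days old at the Cycle 5 dose.
- At the next visit, before Cycle 6, the pre-Cycle 4 value is at least 50 - 3 = 47 days old, so a repeat is always due by then.
- At most one start in each block of three therefore lacks a new value (for example 5, 8 and 11): up to 3 of 12.

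Neither reading reliably gives a creatinine at each cycle start.

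**The case against.** **A dosing condition is not a testing schedule.** Requiring that organ function has recovered could be a hold-and-resume rule applied to the latest available value, and Section 7 tapers chemistries deliberately. But the sentence is not limited to patients with an earlier abnormality, it applies in each cycle, and a site cannot know that recovery is needed without a test.

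**The protocol tolerates an older value at Cycle 1.** Creatinine may be 28 days old at randomization, treatment may start up to ten working days later (about 14 calendar days), and footnote 3 waives a repeat. That makes about 28 + 14 = 42 days, older than the 25 to 34 days at Cycle 5; only Cycles 6, 9 and 12 would exceed it. The arithmetic is right, but the waiver is an explicit exception for Cycle 1 and sets no standard for patients on treatment.

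**Footnote 10 may fill the gap.** The rows marked in the per-cycle column are already done each cycle, so the narrow reading leaves the footnote little to do there. The wide reading would override the three-cycle interval in footnote 3 and would also pull the 12-weekly scans into every cycle. The ambiguity is real, and the wide reading still leaves a gap.

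**The point is small, and the wording could be changed instead.** This stands in part. The adverse-event list is redacted, so the documents cannot show how often creatinine needs checking. Restating Section 5.4 to use the most recent scheduled value would remove the contradiction, but on the narrow reading it would accept a value up to 65 days old at a Cycle 6 start.

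**Conclusion.** The concern holds. From Cycle 5 the dosing rule and the test schedule disagree for creatinine, and only for creatinine. Six of the 12 starts from Cycle 2 to Cycle 13 have no clearly scheduled value if footnote 10 covers only marked rows; up to three can lack a new value if it covers every test. The ages assume cycles within the 3-day window and panels drawn within 72 hours of the cycle.

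This is a minor patient-safety and consistency correction that should be made. It does not touch endpoints, type I error or power, and nothing visible in the documents points to a particular renal risk.

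**What to change.** Require creatinine with the CBC within 72 hours before every cycle from Cycle 2. Amend footnote 3 and the Chemistries entry in the per-cycle column to match; the rest of the panel can stay on its present schedule. State in footnote 10 which tests it covers.

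The change touches two footnotes and one calendar cell. From Cycle 5 it adds two creatinine results per three cycles, on a blood draw already required, with no extra visit or procedure.
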